5.4. Medical History

Medical history collected at the time of entry into the pivotal studies will be coded using the Medical Dictionary for Regulatory Activities (MedDRA) and will be summarized by system organ class (SOC) and preferred term (PT) for the Safety population. Additionally, summaries of uterine fibroid-specific medical and surgical treatment history collected at the time of entry into the pivotal study will be provided. A patient with multiple occurrences of medical history within a PT will be counted only once in that PT. Medical history is not collected in the eCRF of randomized withdrawal study. Adverse events that were collected in the pivotal studies or extension study and ended prior to the start of the randomized withdrawal study will be listed and summarized.

5.5. Prior Medications and Concomitant Medications

Prior medications and concomitant medications taken during this Randomized Withdrawal Study treatment period will be summarized for all patients in the Safety population by randomized treatment group. In addition, concomitant medications taken during the retreatment period will also be summarized for Safety Population by their randomized treatment group. Medications are considered concomitant for randomized treatment period if exposure occurs during the randomized treatment period. Medications are considered concomitant for retreatment period if exposure occurs during the retreatment period. Medications are considered prior if exposure started prior to the date of first dose of randomized withdrawal study drug.

The number and percentage of patients who took at least one dose of a prior or concomitant medication will be summarized by randomized treatment group and overall using the World Health Organization (WHO) Drug Dictionary and summarized according to the Anatomical Therapeutic Chemical (ATC) Classification System and generic medication name. A patient who has been administered several medications with the same preferred medication name will be counted only once for that preferred medication name.

6. STUDY DRUG EXPOSURE AND COMPLIANCE

All analyses of extent of exposure to study drug and compliance will be summarized by actual treatment received in this randomized withdrawal study. Extent of exposure to and compliance with relugolix (or relugolix placebo) and E2/NETA (or placebo) during this randomized treatment period and the retreatment period will be summarized for patients in the Safety population. Exposure to and compliance with relugolix and E2/NETA will be summarized separately and will be based on the drug accountability case report forms.

Study drug exposure summaries will include the total dosages of relugolix and E2/NETA taken in milligrams, the total number of tablets (or capsules) taken, and treatment duration. Total dosages of relugolix and E2/NETA taken during the randomized treatment period and the retreatment period will be summarized by randomized treatment group. Treatment duration during the randomized treatment period and during the retreatment period with any study drug (relugolix, E2/NETA, or placebo) will be summarized by randomized treatment group.

Study drug compliance will be summarized for the randomized treatment period and will be calculated as follows:

$$(\text{total tablets taken} / \text{total tablets expected to be taken}) \times 100$$

The total tablets taken will be calculated as:

$$(\text{total tablets dispensed} - \text{total tablets returned})$$

The total tablets expected to be taken is calculated as the total number of tablets a patient is expected to take each day times the length of time (in days) that the patient was in the randomized treatment period of the study. Tablets that were dispensed and not returned will be assumed to have been taken. For patients who did not return for their last scheduled visit, tablets that were dispensed and not returned will not be included in the calculation of study drug compliance. For patients who did not return for any post-Week 52/Baseline visits and did not return dispensed study drug, study drug compliance will not be calculated and will be categorized as “not able to calculate” in summaries of study drug compliance.

Summary statistics of study drug compliance (eg, mean, median, etc.) will be presented, along with a categorical summary (eg, < 80%, 80% to 100%, > 100%).

The study drug compliance during the retreatment period will be calculated similarly and will be summarized for retreatment period by the randomized treatment group.

7. EFFICACY ANALYSES

7.1. General Considerations

Unless otherwise specified, efficacy analyses will be conducted using the mITT population according to the randomized treatment assignment. Stratified analyses will be stratified by the randomization stratification factors, which include pivotal study baseline menstrual blood loss (MBL) volume (< 225 vs. ≥ 225 mL), geographic region (North America vs. Other, where Europe, Latin America, and Rest of World will be pooled together as Other), and duration of relugolix exposure prior to randomization (28 weeks vs. 52 weeks). If the group of patients at any factor level from a randomization stratification factor (eg, patients with pivotal study Baseline MBL volume ≥ 225 mL) comprises $< 10\%$ of the entire mITT population, this stratification factor (eg, pivotal study Baseline MBL volume) will not be used for stratified analyses. In addition, based on the pooled baseline data, there are < 10 patients in 1 of the 8 strata (derived from the 3 stratification factors each with 2 levels, < 5 patients within a randomized treatment group), geographic region will not be used for stratified analysis. Stratification factors of pivotal study Baseline MBL volume (< 225 vs. ≥ 225 mL) and duration of relugolix exposure prior to randomization (28 weeks vs. 52 weeks) will be used in the stratified analysis for more robust strata-adjusted estimation of treatment effect. The stratification category used at the time of randomization (in the Interactive Web Recognition Service [IWRS] system) will be used for all analyses rather than data recorded on the electronic case report form (eCRF) unless otherwise specified. A sensitivity analysis of the primary endpoint will be performed if the data in the IWRS and eCRF for stratification factors differ by $> 5\%$.

7.1.1. Analyses for Categorical Data

Qualitative variables will be summarized by frequency counts and percentages. Unless otherwise specified, the calculation of proportions will include the missing category. Therefore, counts of missing observations will be included in the denominator and presented as a separate category.

For efficacy endpoints evaluating proportions descriptive statistics (point estimates and corresponding 95% CIs) will be provided by treatment group and visit as appropriate.

7.1.2. Analyses for Continuous Data

This section describes analysis for continuous endpoints in general, not including MBL volume related continuous endpoints. Analyses of change and percent change in MBL volume are described in Section [7.4.2](#).

Continuous variables will be summarized using descriptive statistics (eg, n, mean, median, SD, minimum, and maximum). For the analyses of change from Baseline, the mean at Baseline will be calculated for all patients with at least one post-Baseline value by treatment group. Additionally, the mean of observed results will also be calculated at each visit, including only the patients who are in the analysis population and who have data at that visit by treatment group.

For endpoints evaluating the change (absolute or percent change) from baseline, mean change as well as least squares (LS) mean change and 95% CI will be summarized. LS means and 95% CI will be derived using a mixed-effects model repeated measures approach with treatment,

randomization stratification factors, visit, and treatment by visit interaction included as fixed effects. The Baseline value will be included as a covariate, and an unstructured variance-covariance matrix will be assumed. If the mixed-effects model fails to converge, a first-order autoregressive variance-covariance matrix will be used. Calculation of the dependent variable (change from baseline) for each patient at each visit will be calculated based on the visit windows specified in Section 4.3.7. In addition, summary statistics (LS mean change or LS mean % change) will be graphically presented as appropriate. Note, the mixed-effects models will not be applied to the data analysis during the randomized treatment period due to informative censoring patient's data at the time of retreatment for patients who had MBL volume ≥ 80 mL during the randomized period. They will be applied to data analysis during the cumulative treatment period.

7.1.3. Analyses for Time to Event Data

Time-to-event endpoints will be summarized using the Kaplan-Meier method. The median, quartiles, and probabilities of an event at particular time points will be estimated by the Kaplan-Meier method.

Confidence interval for the Kaplan-Meier estimation is calculated using the exponential Greenwood formula via log-log transformation of the survival function.

A stratified log-rank test will be used to compare relugolix+E2/NETA group to placebo group. Randomization stratification factors (pivotal study baseline MBL volume (<225 mL vs. 225 mL) and duration of exposure to relugolix (28 week vs. 52 weeks)) will be used for the stratified log-rank test..

7.2. Multiplicity Adjustment

The primary and the three key secondary efficacy analyses will be performed at an overall two-sided type I error of 0.05. A test will be deemed statistically significant if the two-sided p-value rounded to 4 decimal places is < 0.05 . If the result of the primary endpoint analysis meets the respective evaluation criterion of the primary endpoint, the key secondary endpoints will then be tested with a fixed-sequence testing procedure to maintain the overall familywise error rate of 0.05 for the testing of primary and key secondary endpoints. The key secondary endpoints with alpha-protection for potential labelling purposes are described in Section 7.4.1. All p-values (if provided) aside from the endpoints listed in the testing order are not adjusted in multiplicity, thus are at a nominal level of 0.05.

7.3. Primary Efficacy Endpoint

The primary efficacy endpoint of the study is the proportion of patients who maintained a menstrual blood loss volume of < 80 mL at Week 76 (24 weeks/EOT of the randomized treatment period) as measured by the alkaline hematin method. The primary endpoint will be referred to as sustained responder rate at Week 76 and defined as the cumulative probability of MBL volume < 80 mL measured while on randomized treatment through Week 76. For the primary analysis, primary endpoint will incorporate the censoring rules described in Section 7.3.1. The primary endpoint of sustained responder rate will be evaluated using the mITT Population.

7.3.1. Primary Efficacy Analysis

The primary hypothesis for the primary efficacy endpoint to be tested in this study is relugolix+E2/NETA group is superior to placebo group with respect to the sustained responder rate at Week 76 based on the MBL volume analyzed by alkaline hematin method:

$$\text{Null hypothesis } H_{01}: \pi^R \leq \pi^P \quad \text{vs.} \quad \text{Alternative hypothesis } H_{a1}: \pi^R > \pi^P$$

where π^R and π^P are the sustained responder rates for relugolix and placebo groups, respectively.

The primary efficacy analysis is the treatment comparison between the relugolix+E2/NETA group and the placebo group performed using a stratified version of the Mantel-Haenszel test statistic for sustained responder rates at Week 76 stratified by baseline mean menstrual blood loss in the pivotal study (< 225 mL vs. ≥ 225 mL), geographic region (North America vs. Other) and the duration of relugolix exposure prior to randomization (28 weeks vs. 52 weeks). In this analysis, the sustained responder rate will be calculated as the Kaplan-Meier estimate of the cumulative probability of MBL volume < 80 mL through Week 76 (Day 169) using the Kaplan-Meier method (see Section 7.3.1.1).

The difference in sustained responder rates between the relugolix+E2/NETA and placebo group and its two-sided 95% CI will be provided.

The study will be considered positive if the treatment effect for the primary endpoint is statistically significant with two-sided p-value < 0.05 .)

For each patient, event status (yes/no) and time to first event (MBL volume ≥ 80 mL) or censoring (if no event) during the randomized treatment period will be derived and used in Kaplan-Meier analysis.

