7.3.1.1. Kaplan-Meier Analysis

The primary endpoint of sustained responder rate at Week 76 will be estimated based on the Kaplan-Meier (KM) survival functions of time to 1st relapse (MBL volume ≥ 80 mL) along with 95% CI for sustained responder rate for each treatment group.

The 95% CI for the KM estimation of the sustained responder rate at Week 76 (Day 169) is calculated using the exponential Greenwood formula via log-log transformation of the survival function.

The 95% CI for treatment difference in sustained responder rates will be calculated via linear transformation of the difference in relapse free survival function with pooled variance, as follows:

$$[(\widehat{S}_R(t) - \widehat{S}_P(t)) - 1.96 \sqrt{\widehat{V}[\widehat{S}_R(t) - \widehat{S}_P(t)]}, (\widehat{S}_R(t) - \widehat{S}_P(t)) + 1.96 \sqrt{\widehat{V}[\widehat{S}_R(t) - \widehat{S}_P(t)]}].$$

Treatment difference in sustained responder rates at Week 76 between relugolix and placebo will be estimated along with 95% CI using the method described below.

Variance of treatment difference will be calculated using the formula:

$$\widehat{V}[\widehat{S}_R(t) - \widehat{S}_P(t)] = \widehat{V}[\widehat{S}_R(t)] + \widehat{V}[\widehat{S}_P(t)];$$

Where each of the variance of the KM estimate will be calculated using the Greenwood's formula

$$\hat{V}[\hat{S}(t)] = \hat{S}(t)^2 \sum_{t_i \leq t} \frac{d_i}{n_i(n_i - d_i)}$$

where n_i denotes the number of patients at risk at time t_i and d_i denotes the number of events observed at time t_i .

P-value for testing treatment difference in sustained responder rates at Week 76 between relugolix+E2/NETA and placebo will be derived using an appropriate test statistic, as described in the following steps.

Step A: The stratified test statistics via log-log transformation of the difference in survival curve at a fixed time point will be used to derive the -value (Klein et al. 2007).

$$x^2 = \frac{\left\{ \sum_{s=1}^M [\log(-\log(\widehat{S}_{R_s}(t))) - \log(-\log(\widehat{S}_{P_s}(t)))] \right\}^2}{\sum_{s=1}^M \left\{ \frac{V(\widehat{S}_{R_s}(t))}{[\widehat{S}_{R_s}(t) \log(\widehat{S}_{R_s}(t))]^2} + \frac{V(\widehat{S}_{P_s}(t))}{[\widehat{S}_{P_s}(t) \log(\widehat{S}_{P_s}(t))]^2} \right\}}$$

Where s is the s^{th} stratum in the total of M strata and $t = \text{Week 76 (Day 169)}$ in this case. Each stratified test statistics at a fixed time under two samples follows a chi-square distribution with one-degree freedom.

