Step B: If the stratified test statistics cannot be calculated due to event having not occurred in certain stratum, unstratified test will be used instead.

Step C: If unstratified test is still not estimable, the stratified version of the Mantel-Haenszel test using pooled KM estimators in each stratum will be constructed as the following. This test statistics follows a chi-square distribution with one-degree freedom.

$$\chi_{MH}^2 = \frac{\left\{ \sum_{s=1}^M \frac{n_{R_s} n_{P_s}}{n_{R_s} + n_{P_s}} (\widehat{S}_{R_s}(t) - \widehat{S}_{P_s}(t)) \right\}^2}{\sum_{s=1}^M n_{R_s} n_{P_s} V(\widehat{S}_{pooled_s}(t))}$$

It is noted that sustained responder rate at Week 104 (Day 365) as a key secondary endpoint will be defined as the KM estimates from the same KM curves and will be analyzed using the same method as described above.

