7.4.1.1. Time to Relapse (Menstrual Blood Loss Volume \geq 80 mL)

For the endpoint of time to MBL volume \geq 80 mL (event) during the randomized treatment period, time-to-event will be defined as weeks from first dose of the randomized withdrawal study drug to first occurrence of MBL volume of \geq 80 mL. The corresponding menstruation start date will be considered as the event date. Patients without an event will be censored by following the same censoring rules described in Section 7.3.1.2. Kaplan-Meier methods will be used to describe the time to event (relapse) distributions for each study treatment group from which median time to event will be derived. Hazard ratio (95%CI) of relugolix + E2/NETA to placebo for risk of relapse (MBL volume \geq 80mL) will be provided using a proportional hazard model stratified by the stratification factors (pivotal study baseline MBL volume (< 225 ml vs. \geq 225 mL) and duration of exposure to relugolix (28 weeks vs. 52 weeks). p-value for comparison of relugolix + E2/NETA to placebo based on the stratified log-rank test will be provided.

7.4.1.2. Proportion of Patients Who Maintained a Menstrual Blood Loss Volume of < 80 mL at Week 104

The proportion of patients who maintained a menstrual blood loss volume of < 80 mL by Week 104 (52 weeks of the randomized treatment period) as measured by the alkaline hematin method will be analyzed using the same method as that for primary efficacy endpoint described in Section 7.3. It is noted that sustained responder rate at Week 104 (Day 365) will be defined as the KM estimates from the same KM curves and will be analyzed using the same method as for the primary endpoint (see Section 7.3.1).

No subgroup analysis will be performed for this secondary efficacy endpoint.

The proportion of patients who maintained a menstrual blood loss volume of < 80 mL will also be summarized during the cumulative treatment period (including both randomized treatment period and the retreatment period).

The proportion of patients who had a menstrual blood loss volume of < 80 mL at a visit will also be summarized descriptively by visit during the cumulative treatment period (including both randomized treatment period and the retreatment period).

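### The SAP defines the primary Week 76 p-value in conflicting ways (8 or 4 strata; Mantel-Haenszel or log-log), and the log-log test it lists first gives every stratum equal weight

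*SAP*

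**What the plan says.** **Strata.** SAP 7.3.1 stratifies the primary test by pivotal-study menstrual blood loss (MBL), "geographic region (North America vs. Other) and the duration of relugolix exposure prior to randomization (28 weeks vs. 52 weeks"). Three two-level factors give 8 strata. SAP 7.1 reports that "there are < 10 patients in 1 of the 8 strata" and concludes that "geographic region will not be used for stratified analysis". It keeps MBL and exposure, which gives 4 strata. SAP 7.1.3 also lists only MBL and "duration of exposure to relugolix (28 week vs. 52 weeks)) will be used for the stratified log-rank test". SAP 7.4.1.1 analyses time to relapse "using a proportional hazard model stratified by the stratification factors (pivotal study baseline MBL volume" and exposure, again without region. Protocol 9.3.1.1 (Amendment 1) plans a Cochran-Mantel-Haenszel test on all three factors.

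**Test.** SAP 7.3.1 says the comparison is "performed using a stratified version of the Mantel-Haenszel test statistic for sustained responder rates at Week 76 stratified by baseline mean menstrual blood loss" and the other factors. SAP 7.3.1.1 then gives three ordered steps for the p-value. For Step A the plan reads "The stratified test statistics via log-log transformation of the difference in survival curve at a fixed time point will be used to derive" it. For Step B it reads "If the stratified test statistics cannot be calculated due to event having not occurred in certain stratum, unstratified test will be used instead". The last resort, Step C, is a Mantel-Haenszel statistic built from Kaplan-Meier estimates; it applies only if Step B also fails.

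**Reach.** SAP 7.3.1.1 applies the same method to the Week 104 sustained responder rate. SAP 7.4.1 makes the primary result the gate for three key secondary tests in fixed sequence.

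**The concern.** A confirmatory trial needs one primary test and one set of strata. Here the test that 7.3.1 names as primary is the last fallback in 7.3.1.1, and the strata in 7.3.1 include a factor that 7.1 removes. Section 7.3.1 refers to 7.3.1.1 for the Kaplan-Meier estimate of the rate. It does not say that the test there replaces its own, and the number of strata M in Step A is left open. Whoever runs the analysis has to choose, and the choice decides whether the trial is positive and whether the key secondary tests open.

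The weighting is a second, separate issue. Step A adds the stratum differences as they are, so a stratum with a few patients per arm counts as much as one with many. Step C weights by stratum size. The two can therefore differ in power, and the planning calculation does not reflect Step A.

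**Working it through.** **1. The instructions side by side**

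| Place | Test for Week 76 | Strata |
|---|---|---|
| Protocol 9.3.1.1 | Cochran-Mantel-Haenszel | MBL, region, exposure (8) |
| SAP 7.3.1 | Stratified Mantel-Haenszel | MBL, region, exposure (8) |
| SAP 7.1 | (general rule) | MBL, exposure (4) |
| SAP 7.3.1.1 | Log-log, then unstratified, then Mantel-Haenszel | M not stated |

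**2. The planning figure.** Inputs from SAP 2.2: 60% versus 40%, two-sided 0.05, 1:1, 360 patients, 20% dropout. Evaluable patients: 360 × 0.8 = 288, or 144 per arm. Pooled two-proportion formula:

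- null SE = √(2 × 0.25/144) = 0.0589
- alternative SE = √((0.24 + 0.24)/144) = 0.0577
- power = Φ((0.20 − 1.96 × 0.0589)/0.0577) = 92.8%

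The stated figure of at least 90% is correct for that test.

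**3. Step A as printed.** With d_s the log-log difference in stratum s and v_s its variance, the statistic is (Σ d_s)² / Σ v_s, with no weights. At 60% versus 40% in every stratum:

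- d = log(−log 0.6) − log(−log 0.4) = −0.584
- variance per arm = (1 − S)/(n_s S (log S)²); both arms together, v_s = 4.341/n_s
- effective n per arm = M² / Σ(1/n_s)
- power = Φ(0.584/√(4.341/n_eff) − 1.96)

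For 90% power, n_eff must be 133.6 per arm, so with 144 evaluable patients only about 7% can be lost to uneven strata. For 4 strata formed from shares a and b, the fraction kept is 16·a(1−a)·b(1−b).

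**4. Power of Step A with 4 strata.** The documents give no stratum shares beyond the one small stratum, so the shares are assumed. The 28-week share is 1/3 except in the first row. Simulations used Kaplan-Meier and Greenwood estimates at Day 169, with 20,000 trials for each configuration in the four uneven rows.

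| MBL ≥ 225 mL share | Fraction kept | n_eff of 144 | Formula, 144/arm | Simulated, 144/arm, no censoring | Simulated, 180/arm, 20% censored |
|---|---|---|---|---|---|
| Equal strata | 1.00 | 144 | 92.0% | 93% | 94–95% |
| 50% | 0.89 | 128 | 88.7% | 90% | 92% |
| 40% | 0.85 | 123 | 87.5% | 89% | 91% |
| 30% | 0.75 | 107.5 | 82.8% | 84% | 87% |
| 25% | 0.67 | 96 | 78.5% | 80% | 83% |

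Mantel-Haenszel gave about 93% (144 per arm) and 95% (180 per arm) throughout. Log-log with inverse-variance weights gave 92% and 94%.

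**5. Same data, opposite verdict at 0.05** (assumed shares, 60% versus 40%)

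- 8-stratum Mantel-Haenszel (7.3.1) versus 4-stratum Step A (7.1 with 7.3.1.1): about 2 to 15% of trials.
- Mantel-Haenszel with 4 versus 8 strata: at most 0.5%.
- Mantel-Haenszel versus inverse-variance log-log, 4 strata: under 1%.

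The disagreement therefore comes mainly from the unweighted sum.

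**6. Step A over 8 strata.** With one stratum of 2 to 4 patients per arm, Step A could not be calculated in 29 to 83% of trials. Power of Step A followed by Step B was 77 to 90%.

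**7. Type I error** (50% versus 50%). With 4 strata: Step A 4.9–5.5%, inverse-variance 4.6–5.0%, Step C 5.0–5.3%. With 8 strata: Step A then B 3.2–3.9%, Step C 5.1–5.6%.

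**8. Step C algebra.** With weight w = nR·nP/(nR+nP), the null variance of w times the stratum difference is nR·nP·V(pooled), which is the printed denominator. Step C is correctly written.

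**The case against.** The strongest reply is that the SAP can be read as one algorithm. Section 7.1 is specific: it gives the sparse-stratum reason, drops region and names the factors kept, and 7.1.3 and 7.4.1.1 follow it. The region clause in 7.3.1 then looks like a carry-over from the protocol. Steps A to C are the only place with formulas for the p-value, and their order is explicit. On that reading the analysis is 4-stratum Step A, and the 8-stratum Step A figures describe something 7.1 rules out. The log-log method is the sponsor's choice with a cited source, and 7.3.1 could be aligned to it without changing the test.

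Part of this stands. The 8-stratum Step A results are a side reading, and region alone hardly moves Mantel-Haenszel. Type I error is controlled with 4 strata, so the weighting costs efficiency, not validity. The power loss needs uneven strata: at equal strata Step A and 4-stratum Mantel-Haenszel disagreed in only 0.3% of trials. It also shrinks with a larger effect. At an assumed 65% versus 40%, Step A power is 94.0–99.0% over the equal and uneven splits and verdicts differ in 0.1–5.4% of trials; at 70% versus 40% they differ in at most 1.1%.

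It does not remove the conflict. Section 7.3.1 is the section that defines the primary analysis, it agrees with the protocol on both the type of test and the factors, and no precedence rule is stated.

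**Conclusion.** The concern holds. The contradiction over strata and test is in the current SAP text and rests on no assumption. It affects the p-value that decides the trial, so it has to be corrected before unblinding; SAP Section 1 itself requires analysis decisions to be made by then.

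The size is conditional. If the effect is 60% versus 40% in every stratum, the two main readings give opposite verdicts in about 2 to 15% of trials over the shares tried. Unweighted Step A falls below the planned 90% once strata are moderately uneven: at an MBL share of about 40% with 144 evaluable per arm, or between 40% and 30% with 180 per arm and 20% censored (28-week share 1/3 in both cases). With near-equal strata the loss is negligible. The sample size calculation is not itself wrong, but it does not describe Step A.

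**What to change.** 1. Delete geographic region from SAP 7.3.1, so that M = 4 and the section agrees with 7.1, 7.1.3 and 7.4.1.1. State M in 7.3.1.1, and record the departure from protocol 9.3.1.1.
2. Name one primary test in the same words in 7.3.1 and 7.3.1.1. Preferred: the size-weighted Mantel-Haenszel statistic now printed as Step C, which is the test 7.3.1 already names. Alternative, if the log-log scale is wanted: Step A with inverse-variance weights, (Σ w·d)² / Σ w with w = 1/v, plus a stated rule for a stratum that cannot be estimated.
3. Keep the unweighted log-log test at most as a sensitivity analysis.
4. Make the same change for the Week 104 sustained responder rate.

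Aligning 7.3.1 to unweighted Step A with 4 strata would end the ambiguity but leave the possible power loss. The cost of the full change is SAP wording and a few lines of code before unblinding, with no new data.
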